Statistical and Analytic Plan	Statistical analyses will be performed using SPSS version 20. Descriptive statistics will describe the incidence of long COVID in participants and its characteristics, the clinical outcome, and the quality of life. The bivariate analysis will be performed using chi-square or fisher , to find the correlation between COVID-19 vaccination status and the characteristics and clinical outcomes of long COVID patients. The value of the limit of significance is 0.05.
Data and Safety Monitoring Plan	If there were any serious adverse events (SAE), the case will be reported to the ethics committee as soon as possible, less than 24 hours from the first time they were discovered, and actions were carried out as quickly as possible until the series of events ends. SAE was written in detail on the SAE form, including the following; when it was first discovered, the manifestation of the incident, the conditions before the incident, the handling of the event, and the outcome.

---

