### 2. Sample Size Calculation

The sample size of this study is obtained from the two-way hypothesis testing formula for the two mean values in two independent groups with a confidence index ( $\alpha$ ) of 95% and power of 80%. Results are considered statistically significant if  $p < 0.05$ . The details of the estimated size of the research subject are as follows:

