#### Analytic study: Prospective Cohort, consecutive sampling method

$$n = \left( \frac{Z_{\alpha}\sqrt{2PQ} + Z_{\beta}\sqrt{P1Q1 + P2Q2}}{P1 - P2} \right)^2 = \left( \frac{1.96\sqrt{2 \times 0.553 \times 0.447} + 0.80\sqrt{0.653 \times 0.347 + 0.453 \times 0.547}}{0.20} \right)^2$$

$$n = 93 \text{ subjects} \rightarrow N = 186 \text{ subjects}$$

Legends:

n : Number of subjects

$Z_{\alpha}$  : Z value in 95% confidence index = 1.96

$Z_{\beta}$  : Z value of test power = 0.80

$P_1 - P_2$  : Minimal difference in proportion considered significant = 0.20 ( $P_1 = 0.653$ )

Q : 1 - P

Assuming a 20% loss to follow-up event, the final sample size is:

$$n = 186 + (186 * 20\%)$$

$$n = 186 + 37$$

$$n = \mathbf{223 \text{ subjects}}$$

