##### **3.2.2. Bivariate analysis**

This analysis is used to see the relationship between the effect of the COVID-19 vaccine on clinical long COVID and the quality of life of long COVID patients. The level of significance used is 0.05. Variables are statistically significant if p-value <0.05. The independent variables in this study are nominal scale, so the test used in this analysis is the chi-square test or fisher's test (in the group of independent variables with a dichotomous scale of 2x2 if the chi-square does not meet the requirements.

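### The readable analysis plan yields only a chi-square or Fisher p-value, which across four vaccination groups gives no direction, size or precision for directional objectives

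*Combined protocol and SAP*

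**What the plan says.** Protocol sections 2.1 and 2.2 set directional aims: whether vaccination could improve clinical outcomes and quality of life, increase exercise capacity, and reduce symptoms, duration and frequency of Long COVID. The synopsis divides 250 subjects into four groups (never vaccinated, first, second and third dose) without giving group sizes.

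The inferential plan is in SAP 3.2.2: "the test used in this analysis is the chi-square test or fisher's test", with "The level of significance used is 0.05" and "Variables are statistically significant if p-value <0.05". The synopsis repeats the threshold ("The value of the limit of significance is 0.05") and gives the purpose of the test as "to find the correlation between COVID-19 vaccination status and the characteristics and clinical outcomes of long COVID patients".

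On description, the synopsis says "Descriptive statistics will describe the incidence of long COVID in participants and its characteristics, the clinical outcome, and the quality of life". It does not say that these summaries are given by vaccination group. SAP 3.2.1 covers the incidence and profile of Long COVID and mentions no interval.

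The only effect size is in the analytic part of SAP section 2: "Minimal difference in proportion considered significant = 0.20", with P1 = 0.653. It is used for planning and does not return in the analysis. A figure under SAP 3.2 is not shown, so these statements concern the readable text.

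**The concern.** A question such as whether vaccination reduces symptoms needs three things in the answer: which way the groups differ, by how much, and how precisely that is known. A chi-square p-value over four groups supplies none of them. Permuting the groups leaves it unchanged, so it cannot separate a dose gradient from its reverse, or one group doing worse from one doing better.

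The plan also does not say how p ≥ 0.05 is to be interpreted. Without an interval, a reader cannot tell a result that rules out a worthwhile difference from one that is merely imprecise. The synopsis expects the study to reinforce the recommendation on vaccine implementation in Indonesia, and a bare p-value is thin support for that in either direction.

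**Working it through.** **Inputs from the documents.** Two-sided alpha 0.05 (Z = 1.96), P1 = 0.653, P2 = 0.653 - 0.20 = 0.453, mean P = 0.553, Z beta entered as 0.80, Long COVID prevalence 0.40 with d = 0.10 (SAP section 2); 250 subjects in four groups (synopsis).

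**Assumptions, since group sizes are not given.** Equal groups: 250/4 is about 62 enrolled, and 250 × 0.80/4 = 50 analysed after the plan's 20% loss. A collapse into two groups gives 250 × 0.80/2 = 100 each.

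**1. The plan's own figure.** n = [(1.96√(2 × 0.553 × 0.447) + 0.80√(0.653 × 0.347 + 0.453 × 0.547))/0.20]² = 93.04, so 93 per group and 186 in total, as printed. The 0.20 is therefore the planning difference.

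**2. The four-group test carries no direction.** Take 62 per group and event counts in dose order, with chi-square on 3 df:

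| Counts | Chi-square | p |
|---|---|---|
| 40/36/32/28 (steady gradient) | 5.21 | 0.157 |
| 28/32/36/40 (reversed) | 5.21 | 0.157 |
| 36/28/40/32 (shuffled) | 5.21 | 0.157 |
| 40/28/40/28 (no dose pattern) | 9.38 | 0.025 |

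The gradient and its reverse give the same p. The pattern without dose order is the one called significant.

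**3. One group worse, the others unchanged.** Take 50 per group, with only the one-dose group differing by 20 points. The non-centrality is n Σ(pᵢ - p̄)²/[p̄(1 - p̄)].

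- For an adverse outcome with rates 0.453/0.653/0.453/0.453, p̄ = 0.503 and Σ(pᵢ - p̄)² = 0.030. The non-centrality is 50 × 0.030/(0.503 × 0.497) = 6.00, and the test is significant 51.8% of the time.
- For a favourable outcome with rates 0.653/0.453/0.653/0.653, p̄ = 0.603. The non-centrality is 1.5/(0.603 × 0.397) = 6.27, and the test is significant 53.8% of the time.

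The p-value alone does not show that the signal is harm. This is one chosen pattern, given as an illustration.

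**4. A non-significant result compatible with 0.20.** Take two groups of 100 with 55% v 45%. Chi-square = 2.00, p = 0.157. SE = √(2 × 0.55 × 0.45/100) = 0.0704, so the 95% CI is 0.10 ± 1.96 × 0.0704, or -3.8 to +23.8 points. At the planned 93 per group, 57 v 45 events (61.3% v 48.4%) gives p = 0.077 and a CI of -1.3 to +27.1 points. Both intervals contain zero and 20 points.

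**5. How often this can arise.** Power for a true 20-point difference between two groups is 78.8% at 93 per group, 61% at 62 and 52% at 50. With four groups, an indecisive pairwise result would be common even if the planned difference were real.

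**6. Descriptive part.** n = 1.96² × 0.4 × 0.6/0.10² = 92.2, so 93, as printed. That formula fixes the half-width of a 95% CI for a proportion: 1.96√(0.4 × 0.6/93) = 0.0996. SAP 3.2.1 never says that this interval will be reported.

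**7. Check on the remedy.** Suppose benefit is declared whenever the interval for any of the three dose groups against never vaccinated lies wholly on the favourable side. With equal groups and no true effect, the chance of at least one false declaration per outcome is about 6% by the normal approximation and about 7% by simulation at 62 per group, against 2.5% for a single contrast. The contrasts therefore need a stated multiplicity position.

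**The case against.** Two-sided testing is normal practice, and SAP section 2 announces it: "two-way hypothesis testing formula for the two mean values in two independent groups". A chi-square test is run on a table of counts. In a 2x2 table, which SAP 3.2.2 mentions, direction can be read from the proportions, and the synopsis plans descriptive statistics for clinical outcome and quality of life. This stands, and it limits the point. A reader might infer that the plan can never show which way an association runs. The documents do not support that, because nothing says the tables will be withheld. What remains is that by-group summaries and their precision are not specified.

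A reader might also infer that a non-significant result will be reported as no effect. No section says so; the documents are silent on how p ≥ 0.05 is interpreted.

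It is tempting, too, to see two conflicting definitions of significance: p < 0.05 in SAP 3.2.2 and 0.20 in SAP section 2. At 93 per group, p < 0.05 is reached at an observed difference of about 1.96√(2 × 0.553 × 0.447/93) = 0.143. With power near 80%, that threshold is always below the difference the study was sized to detect. The 0.20 label is loose wording and not a conflict in the design.

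Finally, vaccination status is observed, so equal groups are unlikely, and confidence intervals around unadjusted contrasts do not deal with confounding. Both remarks are right. The first makes the figures illustrative; the second governs how results should be worded.

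**Conclusion.** The point holds as a gap in what the analysis is specified to deliver. In the readable text the sole inferential output is a p-value judged at 0.05. Over four groups that does not answer directional objectives, and no effect measure, interval, contrast or interpretation rule fills the gap. The size is material: under the stated assumptions, a 10-point observed difference at 100 per group is non-significant while its interval reaches about 24 points, beyond the planning difference. The four-group test is significant about 52% to 54% of the time when only one group is worse by 20 points. These figures rest on equal groups, 20% loss from 250 and, for the first, a collapse to two groups. The gap itself depends on none of these. It should be corrected; the data needed are already being collected.

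**What to change.** **SAP 3.2.2 and the synopsis.**

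- Present each outcome by vaccination group. For each dose group against never vaccinated, give the risk difference and risk ratio (mean difference for questionnaire scores and walking distance) with 95% CI, and the p-value beside it.
- Word results as associations with vaccination status; unadjusted contrasts between observed groups do not support saying that vaccination improved an outcome.
- State either that the three contrasts are estimates without a formal claim, or which multiplicity adjustment applies before any claim of benefit.
- For proportions, report a result as inconclusive when its interval contains both zero and the 0.20 difference of SAP section 2. The documents give no corresponding difference for scores or walking distance, so the SAP should state one if the same rule is to apply there.

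**SAP 3.2.1.** Report the Long COVID proportion with its 95% CI, since the descriptive sample size was set on that precision.

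**Cost.** SAP wording and a little extra analysis, with no new data or subjects. The downside is that some results will read as inconclusive instead of a plain yes or no.

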### **2. Study Objectives**

#### **2.1. Primary**

- To provide an overview of the symptoms and characteristics of Long COVID patients at [name] General Hospital.
- To determine whether vaccination against SARS-CoV-2 could improve clinical outcomes and quality of life of Long COVID patients at [name] General Hospital.

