## 5.4. Data Collection

Data on age, sex, height, weight, body mass index, income, education, comorbidities, smoking, alcohol consumption, documented SARS-CoV-2 vaccination

status (including the amount, type, and when the vaccine was received), detailed history of laboratory-confirmed SARS-CoV-2 infection, Long COVID symptoms, severity, and duration are collected through online screening questionnaire.

Data on quality of life (QoL) are collected through St George's Respiratory Questionnaire (SGRQ) and Short Form (SF)-36 Health Survey self-assessment questionnaire at baseline, 3 and 6 months after enrollment. SGRQ addresses QoL in the domains of symptoms, activity, and impacts within the last 4 weeks; and the SF-36 Health Survey questionnaire addresses QoL in the domains of vitality, physical functioning, bodily pain, general health perceptions, physical and emotional and social role functioning.

Data on functional exercise capacity is measured using the Six-Minute Walking Test (6MWT) at baseline, 3 and 6 months after enrollment. The 6MWT is performed according to the guidelines of the American Thoracic Society (ATS). During the 6MWT, such data are collected: Blood pressure, oxygen saturation (SpO2), heart rate, dyspnea, and overall fatigue score using the Modified Borg scale before and after the test, and also one-time measurement (total distance walked in 6 minutes, symptoms at the end of exercise).

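### Every variable is judged at p<0.05 with no single primary outcome, visit or contrast named and no multiplicity rule, so the overall false-positive rate exceeds 5%

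*Combined protocol and SAP*

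**What the plan says.** The significance rule appears twice. The synopsis (Statistical and Analytic Plan) states "The value of the limit of significance is 0.05", and SAP 3.2.2 applies it variable by variable: "Variables are statistically significant if p-value <0.05". The planned tests are chi-square or Fisher.

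The comparative half of the primary objective (Protocol 2.1) is "To determine whether vaccination against SARS-CoV-2 could improve clinical outcomes and quality of life". Clinical outcomes are not defined further. Quality of life is measured by two instruments (Protocol 5.4). For the first, "SGRQ addresses QoL in the domains of symptoms, activity, and impacts within the last 4 weeks", which is three domains. For the SF-36 the same section lists seven. Both are completed at baseline, 3 months and 6 months. Protocol 2.2 adds exercise capacity, and symptoms, duration and frequency, as secondary. Vaccination status has four categories.

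The sample-size section does not identify a primary outcome either. SAP 2 announces a "two-way hypothesis testing formula for the two mean values in two independent groups", but the formula that follows compares two proportions, 0.653 and 0.453, of an outcome that is not named.

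Nothing in the readable text gives a primary visit, a primary contrast, a testing order or an adjustment for multiple tests. The figure under SAP 3.2 is not shown, so its content is unknown.

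**The concern.** A rule that calls each variable significant at 0.05 limits the error of one test. It does not limit the chance that some variable among many crosses the line when vaccination has no association with any of them.

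This matters because the study is not purely descriptive. The descriptive part has its own section (SAP 3.2.1), and 3.2.2 is the inferential part. The objectives are worded as questions to be decided, Protocol 5.5 states the direction the investigators expect, and the synopsis rationale hopes the results will strengthen the case for vaccine implementation. With an expected direction and no outcome fixed in advance, a chance result on one scale at one visit could be read as an answer to the primary question, and the plan offers no basis for telling the two apart.

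**Working it through.** **The plan's own figure.** The documents state no overall error rate. The nearest stated figure is the analytic sample size, which shows what one test at 0.05 was planned for. With P = (0.653 + 0.453)/2 = 0.553:

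- 1.96 × √(2 × 0.553 × 0.447) = 1.378
- 0.80 × √(0.653 × 0.347 + 0.453 × 0.547) = 0.551
- n = ((1.378 + 0.551)/0.20)² = 93.04, so 93 per group and 186 in total. Then 186 × 1.2 = 223.2, so 223.

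The plan's 93, 186 and 223 are reproduced. They describe a single two-sided test of one binary outcome between two groups. (The formula uses 0.80 where the z value for 80% power is 0.842, which would give 96 per group. That does not affect this point.)

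**Inputs for the error rate.**

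- Level per test: 0.05, from SAP 3.2.2.
- Quality-of-life domains: 3 SGRQ + 7 SF-36 = 10, from Protocol 5.4.
- Secondary outcomes: walk distance, symptoms, duration and frequency = 4, from Protocol 2.2 and 5.4, giving 10 + 4 = 14.
- Follow-up visits: 2 (3 and 6 months), giving 14 × 2 = 28.
- Number of tests actually intended, and correlation between them: not given. Both are assumptions here. The range taken is 2 to 28 tests and correlation 0 to 0.8, with one test per outcome per visit.

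**Formulas.** Under no association, for k independent tests: 1 − 0.95^k. For tests with equal correlation ρ, write each statistic as √ρ·U + √(1−ρ)·E, with U shared and E separate for each test, and find the chance that at least one of the k exceeds 1.96 in absolute value. The correlated case treats each statistic as normal. That is an approximation for a four-group chi-square.

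**Results: chance of at least one p<0.05, either direction.**

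| Tests (k) | What is counted | Independent | ρ = 0.5 | ρ = 0.8 |
|---|---|---|---|---|
| 1 | one named primary test | 5% | 5% | 5% |
| 2 | one clinical, one quality-of-life variable | 9.75% | 9% | 8% |
| 10 | quality-of-life domains, one visit | 40% | 29% | 17% |
| 14 | plus four secondary outcomes, one visit | 51% | 35% | 20% |
| 28 | all 14 at both follow-up visits | 76% | 49% | 25% |

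The independent column is 1 − 0.95² = 0.0975, 1 − 0.95¹⁰ = 0.401, 1 − 0.95¹⁴ = 0.512 and 1 − 0.95²⁸ = 0.762.

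**Apparent benefit only.** Counting only results that favour vaccination (0.025 each, independent), 10 tests give 1 − 0.975¹⁰ = 22% and 14 give 1 − 0.975¹⁴ = 30%, against 2.5% for one test. At correlation 0.5, 14 tests give 17%. This is approximate, because a four-group chi-square has no single direction.

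Pairwise contrasts between dose groups would add tests to every row.

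**The case against.** The best reply is that the plan never commits to this many tests. SAP 3.2.2 refers only to two constructs, clinical long COVID and quality of life. Protocol 5.4 describes what each questionnaire covers and does not make each domain an endpoint. Chi-square and Fisher tests need categories, so the scores would first have to be grouped in some unstated way. Domains answered by the same patient are likely to be positively correlated. The plan also separates primary from secondary objectives, speaks of relationship and correlation, and gives half of its primary objective to description.

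Much of this stands, and it rules out three stronger readings:

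- A reader might infer that a false claim is about as likely as not. That needs roughly 14 independent tests (log 0.5 / log 0.95 = 13.5). The documents support neither the count nor independence, and the figure counts results in both directions.
- A reader might count walk distance and symptoms, duration and frequency as part of the primary objective. Protocol 2.2 puts them under secondary, so for the primary objective the explicit list is the 10 questionnaire domains plus clinical outcomes left undefined.
- A reader might infer that any one p<0.05 would be reported as vaccination improving Long COVID. No passage contains such a reporting rule. The plan permits that reading but does not state it.

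The reply does not remove the point. Even on the narrowest reading, two variables, the error is 8% to 10%. An unstated number of tests also leaves the choice open until after the data are seen.

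**Conclusion.** The point holds as a gap in error control whose exact size cannot be fixed from the documents. Under every count of two or more tests and every correlation examined, the chance of at least one false positive exceeds the nominal 5%. For the listed quality-of-life domains at one visit it is roughly three to eight times nominal (17% to 40%).

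These figures assume one test per outcome per visit, a two-sided 0.05 for each, equal correlation between 0 and 0.8, and no true association. They would change if the figure missing under SAP 3.2 contained a testing hierarchy. They say nothing about confounding by vaccination status, which could produce associations without any chance error and needs separate treatment. The plan should be changed on this point, but the defect does not make the study unworkable.

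**What to change.** In SAP 3.2.2, name one primary outcome, one visit and one group contrast, and state that the 0.05 limit and the words statistically significant apply to that test alone. The natural choice is the binary outcome and two-group contrast behind 0.653 and 0.453 in the sample-size calculation. The sponsor needs to say what that outcome is and how the four vaccination categories form the two groups. This keeps the planned chi-square test and the existing sample-size basis, and returns the false-positive rate of the primary claim to 5%.

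Report all other outcomes as estimates with 95% intervals, or with Holm-adjusted p-values. For scale, holding 14 outcomes jointly at 5% by Bonferroni would need 0.05/14 = 0.0036 per test.

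If a continuous score is preferred as primary, such as a questionnaire score across four dose groups, a change of wording is not enough. The test must change from chi-square or Fisher, and the sample-size basis must be restated to match.

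The cost of the preferred route is SAP text, with no new data, visits or subjects. The downside is that some secondary results can no longer be called significant.

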#### **2.2. Secondary**

- To determine whether vaccination against SARS-CoV-2 could increase functional exercise capacity of Long COVID patients at [name] General Hospital.
- To determine whether vaccination against SARS-CoV-2 could reduce symptoms, duration, and frequency of Long COVID at [name] General Hospital.

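### The only test visible in the plan, chi-square/Fisher, is chosen from the scale of the exposure, so quality-of-life scores can in practice be tested only after cuts that the visible text does not define

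*Combined protocol and SAP*

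**What the plan says.** SAP 3.2.2 (Bivariate analysis) covers the effect of vaccination "on clinical long COVID and the quality of life of long COVID patients". Its reason for the test is "The independent variables in this study are nominal scale, so the test used in this analysis is the chi-square test", or Fisher's test for 2x2 tables where chi-square requirements are not met. The synopsis (Statistical and Analytic Plan) names the same two tests "to find the correlation between COVID-19 vaccination status and the characteristics and clinical outcomes of long COVID patients". No other inferential method appears in the visible text. The figure under SAP 3.2 and the flow diagram under SAP 4 are not shown.

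The outcomes at issue are these:

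- **Quality of life.** Protocol 2.1 makes it part of a primary objective: "To determine whether vaccination against SARS-CoV-2 could improve clinical outcomes and quality of life of Long COVID patients". Protocol 5.4 measures it with the SGRQ and the "Short Form (SF)-36 Health Survey self-assessment questionnaire at baseline, 3 and 6 months after enrollment".
- **Exercise capacity.** Protocol 2.2 has the secondary objective "To determine whether vaccination against SARS-CoV-2 could increase functional exercise capacity of Long COVID patients". Protocol 5.4 states: "Data on functional exercise capacity is measured using the Six-Minute Walking Test (6MWT) at baseline, 3 and 6 months after enrollment". The total distance walked is recorded.

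Protocol 5.4 also collects possible adjustment variables, beginning "Data on age, sex, height, weight, body mass index, income, education, comorbidities, smoking, alcohol consumption".

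SAP section 2 introduces its calculation as one for two means, then sizes the analytic part on two proportions (0.653 and 0.453) without saying which outcome they describe.

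**The concern.** A nominal exposure does not by itself determine the test. With vaccination groups as the exposure, a categorical outcome leads to chi-square or Fisher, and a numerical outcome leads to a comparison of means or ranks, or to a regression. SAP 3.2.2 considers only the exposure and applies the result to quality of life.

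Three things follow if the rule is used as printed:

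1. SGRQ and SF-36 scores must be put into categories before they can be tested, which discards information.
2. The result depends on a cut that the visible text leaves open. A cut chosen after the data are seen would raise the false-positive rate.
3. A reader cannot tell whether the result will describe status at one visit or change over 6 months, although three visits are collected.

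Walk distance is in the same position if it counts among the clinical outcomes in the synopsis. If it does not, the visible text assigns it no test.

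**Working it through.** **Inputs.** From SAP section 2: P1 = 0.653, P2 = 0.453, Z-alpha = 1.96, Z-beta printed as 0.80, 93 per group, and a Long COVID prevalence of 0.40 in the descriptive calculation. From the synopsis: 250 subjects. The documents give no SD or minimal difference for SGRQ, SF-36 or walk distance, so a normal score with equal SDs and two equal groups is my assumption.

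**1. The plan's own figure.** P = (0.653 + 0.453)/2 = 0.553 and Q = 0.447.

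- 1.96 × √(2 × 0.553 × 0.447) = 1.378
- √(0.653 × 0.347 + 0.453 × 0.547) = 0.689
- n = [(1.378 + 0.80 × 0.689)/0.20]² = 93.04, which matches the stated 93 per group and 186 in total.

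With the normal quantile for 80% power, 0.842, the same formula gives 96 per group. That is a separate matter and the point does not rest on it.

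**2. The same difference as a shift in a score.** If the two proportions came from cutting a normal score, the shift is z(0.653) − z(0.453) = 0.393 + 0.118 = 0.51 SD.

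**3. Power after the cut and without it.**

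- Cut: Φ[(0.20√n − 1.378)/0.689].
- Uncut: two-sided t-test with noncentrality 0.512 × √(n/2).

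| Analysed | n per group | Cut | Uncut |
|---|---|---|---|
| The plan's 186 subjects | 93 | Φ(0.80) = 79% | noncentrality 3.49: 93% |
| Long COVID only, 250 × 0.40 = 100 | 50 | Φ(0.05) = 52% | noncentrality 2.56: 72% |

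The second row is there because SAP 3.2.2 speaks of Long COVID patients, while the eligibility criteria in Protocol 5.2 do not require Long COVID. It makes no allowance for loss to follow-up. For 80% power the cut analysis needs 96 per group and the uncut analysis 61, a ratio of 61/96 = 0.64. This agrees with the known efficiency of a median split of a normal score, 2/π = 0.637.

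**4. How much the place of the cut matters.** For the same 0.51 SD shift at 93 per group, power is about 79% with the cut near the median, 75% at 70/30, 67% at 80/20, 51% at 90/10 and 36% at 95/5.

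**5. A cut chosen after seeing the data.** I simulated 40,000 trials with no group difference, 93 per group, and counted a trial as positive if uncorrected chi-square gave p < 0.05 at any of the three population quartiles. About 12% were positive, against a nominal 5%. With continuity correction the figure is about 8.5%.

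**The case against.** **A categorical outcome may be intended.** The sample size rests on proportions, and a responder analysis tested by chi-square would be legitimate. If that outcome is truly binary, nothing is lost. This stands as a possibility. But the proportions are not tied to any outcome, and the same section speaks of two means, so section 2 does not settle it.

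**The missing figure may supply tests, categories or visits.** This also stands for whatever is absent from the text, and it limits confidence. It does not repair the reason printed in SAP 3.2.2, which is incomplete whatever the figure shows.

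**Scores may still be described without cuts.** The synopsis plans descriptive statistics for quality of life. The information loss therefore concerns the test and need not affect all reporting.

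**Chi-square can be run on uncut scores.** Literally it can, but the table would be sparse and the order of the scores ignored. In practice cuts are needed.

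**The power figures are not the plan's.** Correct. There are four vaccination groups of unstated size, and the analysis population is not stated. The direction of the loss holds in both rows of the table; the exact values rest on the assumptions.

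A reader might infer that the investigators mean to look for a favourable cut. Nothing in the documents says so. The 12% shows what an open cut would permit and does not predict what will be done.

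**Conclusion.** The point holds for the visible text. The rule in SAP 3.2.2 chooses the test from the exposure alone and applies it to quality of life, so numerical scores behind a primary objective would have to be tested through categories that the visible text does not define. Walk distance has the same gap or no test.

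The best single measure of the cost is the 64% of information kept by a median split of a normal score; a cut further from the middle costs more. The loss of about 14 percentage points of power at 93 per group, or about 20 at 50 per group, is illustrative. It assumes a normal score, a 0.51 SD shift and two equal groups.

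Two stronger conclusions are not supported. One is that the primary analysis is invalid: a responder analysis with its cut and visit fixed in advance would be valid, though less efficient if it came from cutting a numerical score. The other is that the study as planned is underpowered for quality of life: the documents give neither the SD nor the target difference needed to judge that.

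This should be changed before analysis. Confidence is moderate because of the missing figure.

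**What to change.** In SAP 3.2.2, and to match in the synopsis:

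1. Choose the test by the scale of the outcome.
2. Analyse SGRQ scores, SF-36 domain scores and walk distance as numerical outcomes that use the repeated visits. One option is a linear mixed model with vaccination group, visit and group × visit; another is a baseline-adjusted regression at 6 months. Adjust for covariates already collected under Protocol 5.4, and report an adjusted association with its 95% CI.
3. State whether the analysis covers all subjects or only those with Long COVID.
4. Name one primary score, visit and group contrast in advance.
5. Keep chi-square/Fisher for truly categorical outcomes, and fix the cut-off and visit of any responder analysis in advance.
6. In SAP section 2, say which outcome the proportions describe, and that they do not size the numerical analysis.

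The cost is SAP wording and a modest amount of extra analysis: residual checks, and a transformation or robust method if scores are skewed. The scores, distances and covariates are already collected, and enrolment need not change. If the missing figure already gives some of this, it should be carried into the text and reconciled with 3.2.2.
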